2.3.2 KNOWN POTENTIAL BENEFITS

Participating children will receive dental screenings by University of Iowa (UI) providers who are authorized, trained, and calibrated to make caries diagnosis. Mothers will receive oral and written information about their children's caries status when they are ages 12, 24, and 36 months.

2.3.3 ASSESSMENT OF POTENTIAL RISKS AND BENEFITS The potential benefits of the study outweigh the risks.

(2b) To test the degree to which the intervention produces its effects on children's oral health status through its mediating effects on mothers' changes in behaviors concerning their child's oral health (i.e., oral hygiene habits, dietary habits, use of fluoride, visits to the dentist, lift-the- lip to check for early signs of cavities)	behaviors toward the child's oral health will be assessed through a series of questions (i.e., visit to the dentist, detailed dietary and oral hygiene habits, etc.)	(2b) The same questionnaires were used and validated in several previous research projects from the research team. ^{10-13,50-} ⁵⁵	(2b) According to SDT, the greater the extent to which the autonomy- supportive message allows mothers to experience autonomy support and volitional internalization, the more positive will be the mothers' post-message oral health care motivation (need satisfaction, autonomous motivation), behavioral care for their children . In other words, mothers of high-risk children who receive our videotaped autonomy- supportive messages, compared to mothers of high-risk children who receive only videotaped neutral messages, will demonstrate more positive changes

OBJECTIVES	ENDPOINTS	JUSTIFICATION FOR ENDPOINTS	PUTATIVE MECHANISMS OF ACTION
	and nine-month follow-ups. *At the final visit (Visit 4), behavior questions will assess the key topics discussed previously at all three time points.		regarding behaviors towards their children's oral health, such as more positive oral hygiene and dietary habits, use of fluoride, visits to the dentist, lift-the-lip to check for early signs of cavities, etc.
(2c) To test the degree to which the intervention improves other indicators of oral health status in children (levels of salivary MS ^a and visible plaque ^b scores among the children).	all participating	was used and validated in several previous research projects from the research team. ^{10-13,50-} ⁵⁵	(2c ^a) According to SDT, the greater the extent to which the autonomy- supportive message allows mothers to experience autonomy support and volitional internalization, the more positive will be the mothers' post-message oral health care motivation (need satisfaction, autonomous motivation), knowledge and behavioral care for their children. These gains in the mother's oral health care motivation, knowledge, behaviors, and self- efficacy will be the active ingredients during mother-child interactions that produce longitudinal gains in the children's oral health outcomes as evidenced by lower levels of salivary MS . In other words, mothers of high-risk children who receive our videotaped autonomy-supportive messages, compared to

OBJECTIVES	ENDPOINTS	JUSTIFICATION FOR ENDPOINTS	PUTATIVE MECHANISMS OF ACTION
			mothers of high-risk children who receive only a videotaped neutral messages, will gain greater capacity and skill to provide their children with high- quality oral health care. Consequently, their children will have lower levels of salivary MS.
	(2c ^b) Each child will be examined at 12, 24 and 36 months of age	was used and validated in several previous research projects from the research team. ¹⁰⁻	(2c ^b) According to SDT, the greater the extent to which the autonomy- supportive message allows mothers to experience autonomy support and volitional internalization, the more positive will be the mothers' post-message oral health care motivation (need satisfaction, autonomous motivation), knowledge and behavioral care for their children. These gains in the mother's oral health care motivation, knowledge, behaviors, and self- efficacy will be the active ingredients during mother-child interactions that produce longitudinal gains in the children's oral health outcomes as evidenced by lower levels of visible plaque . In other words, mothers of high-risk children who receive our

OBJECTIVES	ENDPOINTS	JUSTIFICATION FOR	PUTATIVE
		ENDPOINTS	MECHANISMS OF
			ACTION
			videotaped autonomy-
			supportive messages,
			compared to mothers of
			high-risk children who
			receive only a
			videotaped neutral
			messages, will gain a
			greater capacity and skill
			to provide their children
			with high-quality oral
			health care.
			Consequently, their
			children will have lower
			levels of visible plaque.

4 STUDY DESIGN

4.1 OVERALL DESIGN

This UH3 clinical trial study constitutes a Stage II research according to the NIH Stage Model.⁴ The study design specifies a two-arm, randomized controlled clinical trial to assess the effectiveness of autonomy-supportive videotaped oral health messages informed by SDT as a means of preventing ECC, as compared to the effects of exposure to neutral messages also delivered via videotape. The intervention is intended for use in public health settings attended by high-caries risk groups, and the proposed UH3 clinical trial will be conducted at several WIC clinic sites in different rural and urban counties in Iowa with relatively large Hispanic and African-American populations.^{51,52}

The study sample will consist of 634 pregnant women whose future children will be followed until they are 36 months of age. Pregnant women, between 12 and 36 weeks of the gestational period, 18 to 45 years old, and with no intention to move away in the next four years will be eligible to participate in the study. Recruitment will occur anywhere between 12 to 36 weeks of gestation. However, study interventions will only start between 16 to 36 weeks of gestation. If a pregnant woman is recruited between 16 to 36 weeks of gestation, the study procedures can begin immediately. If the woman is recruited between 12 to 15 weeks of gestation, we will schedule her an initial study visit for later, that is between 16 to 36 weeks of the gestation period. At their first study visit, informed consent will be obtained. After informed consent, they will be randomly assigned to one of two study groups: Group 1 (experimental (SDT) group) and Group 2 (neutral control group). The primary outcome of interest will be children's caries status. Secondary outcomes will be changes in children's oral health behaviors conducive to better oral hygiene and dietary habits, as well as lower levels of dental plaque and MS.

The central hypothesis is that a theory-based intervention approach using videotaped messages and targeted to mothers of high-risk young children will promote an elevated sense of perceived autonomy, competence, and relatedness, which will in turn lead mothers to experience and demonstrate improved self-reported knowledge, behavioral intention and subsequent behavior concerning their child's oral health. Consequently, their child will have more positive oral health outcomes, such as lower levels of caries, dental plaque, and MS. We predict that the theory-based intervention will enhance mothers' oral health care knowledge (Hypothesis 1) and behavior toward their oral health and their child's oral health (Hypothesis 2), relative to neutral messages, also delivered via videotapes. In addition, these hypothesized benefits will apply to both short-term (one-month) and long-term (nine-month) effects across each time point (prenatal, Age 1-2, Age 2-3, Age 3+).

4.2 SCIENTIFIC RATIONALE FOR STUDY DESIGN

The strategy of providing caretakers with autonomy support has been shown to produce very large effect sizes across multiple domains.^{23,25,56} There is a need to evaluate the effectiveness of a theory-based intervention to alleviate the ECC burden using a psychological theory of motivation, such as SDT, proven useful in promoting behavior change in several domains.^{3,24,25,34}

4.3 JUSTIFICATION FOR INTERVENTION

The mode of our intervention delivery is through videotaped oral health messages presented through a link on a tablet at the WIC clinic sites or through a participant's smart phone between site visits. This intervention delivery provides a cost-effective behavioral approach targeted to ECC prevention and does not depend on the availability of either dental and/or medical professionals to deliver the oral health messages. Empirical research, including our own preliminary work, has shown this particular video-based autonomy supportive intervention (SDT) to be accepted by WIC mothers and effective in ECC-prevention.⁵⁰ Our prior focus groups reported that the video length along with images and messages were both appealing and understood by the WIC mothers. The mothers also felt the videotaped oral health messages represented different ethnic groups and reflected their own life experiences.

The literature supports supplemental follow-up activities in boosting the original intervention experience to reinforce the oral health message.⁵⁷ Therefore, mothers will receive a 3-month booster message via link through their smart phone after each oral health message received at their study WIC visits 1, 2 and 3. Viewing of the 3-month booster message is optional.

The minimum-acceptable participation in order to have evaluable data on the study primary outcome would be the first and last visits. At the last visit, children will be examined for their caries status, therefore participation in this visit will be essential to assess the overall effectiveness of our intervention on ECC prevention. Ideally, the participants will complete the four WIC site visits, as well as study activities at 1-, 3- and 9 months post WIC visits to access their changes in knowledge and behavior towards their child's oral health, as well as retention and continued use of the information presented at each intervention.

4.4 END-OF-STUDY DEFINITION

The end of the study is defined as the date when the last participating mother-child dyad completes study activities for the last visit (Visit 4).

5 STUDY POPULATION

5.1 INCLUSION CRITERIA

- 1) WIC-participating pregnant women who are 18 to 45 years old.
- 2) Between 12 and 36 weeks of the gestational period.
- 3) Able to speak, understand and read English or Spanish
- 4) No intention to move away in the next 4 years.

5.2 EXCLUSION CRITERIA

3) Mothers who deliver their child prior to their first study intervention visit.

5.3 LIFESTYLE CONSIDERATIONS

NA

5.4 SCREEN FAILURES

Screen failures are defined as participants who consent to participate in this study and do not meet one or more inclusion criteria and/or do meet the exclusion criteria for participation in this trial (screen failure). Examples include a pregnant woman giving birth prior to the first intervention visit or not being fluent in either English or Spanish languages, in which case she would no longer be eligible for the study. Each potential screen failure will need to be determined on a case-by-case basis.

5.5 STRATEGIES FOR RECRUITMENT AND RETENTION

We plan to assess our recruitment rate during months three through 12 after the clinical trial starts. If the pace of recruitment is slow, we will increase recruitment days, advertise our study more aggressively through posters and media avenues, recruit participants from additional WIC sites, and/or consider increasing the incentives given to participating mothers and children. We will assess our retention rates annually at months 12, 24 and 36 of follow-up. If our follow-up exam rate is below the expectancy, then we plan to adopt the same methods described above for recruitment, as well as conduct the study at WIC sites that provide services on Saturday mornings. With four dental examiners, we will be able to increase the number of exam days, allowing mothers more flexibility in scheduling their study visits, improving retention and helping us finish the study on time.

Study staff will recruit subjects at all participating WIC sites on targeted clinic days. The CTRA and research assistants (RAs) will work to create schedules whereby specific days are chosen based on WIC site schedule and attendance patterns in order to maximize the number of WIC clients successfully recruited. Verbal and written information will be provided to prospective participants, and upon obtaining consent, subjects will be enrolled in the study. In some cases, for pregnant women who express interest but decline enrollment at that time, contact information will be gathered and follow-up emails/text messages and telephone calls made in an attempt to secure their enrollment in the study. In addition to the recruitment described above, WIC study staff will provide an informational brochure to each client who meets inclusion criteria, with WIC staff collecting names, home addresses/telephone numbers, and emails from interested

women (after the women give permission for sharing the information). The WIC staff will then forward this information to study staff who will call the mothers directly to 1) provide a brief overview of the study and introduce the potential risk and benefits of participation, 2) determine interest in study participation, and 3) if they are interested, schedule an initial appointment, at which time formal enrollment will take place and informed consent obtained. The study brochures and posters will be placed at the WIC sites will provide a QR code linking to a contact sheet that mothers can directly fill out to allow study team members to follow-up and contact them.

In order to increase retention, every attempt will be made to maintain contact with all study participants during the clinical trial period through bi-annual study newsletters, multiple phone calls, texts, and emails, along with personal cards to provide valuable communication and continued support with the participants (i.e., congratulate mothers on the baby's birth, mother's and child's birthdays, Mother's Day, thank you notes, etc.). We will create social media contacts through a Birth to Three Cavity Free Facebook study account, and ensure all participants are sent individual, direct messages to prevent information sharing between participants. All of these efforts are crucial to maintaining our cohort of participants.

For all study participants, phone, text, email and/or mail contacts will be made to schedule forthcoming assessment appointments and keep participants engaged in the study. Contacts will include newsletter with updates about the study, as well as thanking the participants. In order to enhance continuing participation in this study, the participants will be verbally encouraged to combine their regular WIC appointments with their visits for this study. In addition, a phone call and text message through REDCapTM (Research Electronic Data Capture) will occur to every participant one week prior to each scheduled appointment to remind them about the time and location, as well as a text message a day before to confirm their appointment attendance. If a WIC appointment is missed, mothers will be allowed up to 2 months to reschedule any of the inperson WIC site visits. If mother's misses the 2-month time window, she will not be able to continue the follow-up questionnaires until the next yearly WIC visit.

Mother's will have up to eight weeks to complete the one- and nine-month questionnaires via REDCapTM, with weekly reminders to complete them. If mothers do not complete the questionnaires after the first three reminders, REDCapTM will notify the study team, and an RA will contact the mother to complete the questionnaires. Non-responders will also be mailed paper copies of the questionnaires with a prepaid and self-addressed envelope to return once completed.

Due to the time spent at each study visit (~1.5 hours) to complete all study procedures (i.e. consent forms, pre- and post-questionnaires, view video messages, dental examination, etc.), incentives for the subjects will include dispensing of toothbrushes, fluoride toothpaste and a small toy at each visit for the study children and a gift card to the study mothers. Monetary gift cards will be given to participants after completing study visits and returning questionnaires at each one- and nine-month time points as it follows:

Visit 1 (Prenatal): \$50 1-month follow-up questionnaires: \$20 9-month follow-up questionnaires: \$20 Visit 2 (age 1 to 2): \$75 1-month follow-up questionnaires: \$20 9-month follow-up questionnaires: \$20 Visit 3 (age 2 to 3): \$100 1-month follow-up questionnaires: \$20 9-month follow-up questionnaires: \$20 Visit 4 (age 3+): \$125

If needed, a no-cost extension to allow more time to complete the study will be sought.

6 STUDY INTERVENTION(S) OR EXPERIMENTAL MANIPULATION(S)

6.1 STUDY INTERVENTION(S) OR EXPERIMENTAL MANIPULATION(S) ADMINISTRATION

6.1.1 STUDY INTERVENTION OR EXPERIMENTAL MANIPULATION DESCRIPTION

This is a two-arm, randomized controlled clinical trial (NIH Stage II Research Model)⁴ to assess the effectiveness of autonomy-supportive videotaped oral health messages informed by SDT as a means of preventing ECC, as compared to the effects of exposure to neutral messages also delivered via videotape. The intervention is intended for use in public health settings attended by high-caries risk groups. Enrollment may take as long as 18 months but is likely to require significantly fewer months to meet recruitment goals.⁵⁴ Study participation will last approximately 3½ years. Subjects, clinical examiners and statistical analysts will be blinded with respect to treatment allocation; care will be taken to maintain allocation concealment. Treatment allocation will be based upon a randomization schedule (to groups 1 or 2 provided by REDCapTM). In addition to the study CTRA, RAs will not be blinded, so that they can deliver the assigned intervention as a supervised exposure to prevent contamination, as a further measure to ensure rigor and transparency.

6.1.2 ADMINISTRATION AND/OR DOSING

- Mothers will be randomly assigned to either an experimental (SDT) group (Group 1) where mothers will receive SDT-informed autonomy-supportive messages or a control (neutral) group (Group 2) where mothers will receive the same oral health care messages delivered using a neutral style.
- All mothers will be exposed to a series of three videotaped oral health messages during pregnancy, and then when their child is 12 and 24 months of age.
 - The first videotaped message will be shown during the prenatal period and will cover a variety of oral health topics regarding the pregnant women's own oral health, the impact of their general and oral health on their future child's oral health, and oral health issues focused on specific needs for children 0 to 12 months of age.
 - The second videotaped message will be shown when the child is 12 months of age and cover oral health issues focused on specific needs for children 12 to 24 months of age.
 - The third videotaped message will be shown when the child is 24 months of age and cover oral health issues focused on specific needs for children 24 to 36 months of age.
- The oral health messages in all three videos for the experimental group (Group 1) will be informed by the SDT. All videos for the experimental (SDT) group (Group 1) will cover a variety of oral health topics: the impact of the mother's oral health on their children's oral health, process of tooth decay, oral hygiene practices, dietary habits that affect caries susceptibility, and checking the child's teeth for early signs of cavities (white spot lesions). Throughout the videos, motivation messages will address the harm of inappropriate oral hygiene and dietary habits, challenges mothers face in caring for their

child's oral health, and tips for positive oral health practices. These messages will be communicated in an autonomy-supportive way.

- All videos for the control (neutral) group (Group 2) will cover the same dental content presented in the videotaped messages for the experimental (SDT) group (Group 1); however, the message will be delivered using a neutral style and will be simply informative.
- Prior to watching the videotaped messages at visits 1, 2 and 3, participating women from both groups will complete a series of pre-intervention questionnaires regarding their own oral health and their (future) child's oral health. The questionnaires will include information regarding the mother's (1) demographics; (2) perceptions and status of their own oral health; and (3) pre-intervention self-reported knowledge and behavior concerning their own oral health (dietary/oral hygiene behaviors, frequency of visits to the dentist, etc.), as well as concerning their child's oral health (child's dietary/oral hygiene habits, etc.).
- Immediately after viewing the videotaped oral health messages at visits 1, 2 and 3, participating women from both groups will complete two additional questionnaires to assess their perceptions of the degree of autonomy support of the videotaped messages. One questionnaire will assess the mothers' perceived feelings of autonomy, relatedness, and competence ("health care climate questionnaire"), and the other will assess the mother's internalization of the videotaped message (i.e., the degree to which mothers understood, agreed with, and perceived the oral health message as helpful and useful to them ["internalization questionnaire"]).
- SDT proposes that, if the participating woman has internalized the message, the changes should be evident within a short period of time.⁷ Thus, participating women from both groups will be asked to complete post-intervention questionnaires at *one-month follow-up* after viewing the videotaped messages at visits 1, 2 and 3 designed to assess mothers' changes in self-reported knowledge and subsequent oral health behavior towards their child's oral health. According to the informed consent approved by the UI IRB, "You (study participant) may feel uncomfortable in answering certain questions and you can choose to decline any aspect of the study at any time. You and your child may discontinue participating at any time without any negative consequences." Therefore, participants may choose not to complete the one-month follow-up questionnaires.
- Booster messages will be sent to mothers at *three-month follow-up* after viewing the videotaped oral health messages at visits 1, 2 and 3 to help them overcome the difficulties of adopting the suggested behaviors. The booster messages for mothers of Group 1 will be autonomous-supportive, while neutral for mothers of Group 2. Viewing of the 3-month booster message is optional.
- In order to assess long-term behavioral changes, all study mothers will be asked to complete again the post-intervention questionnaires at *nine-month follow-up* after viewing the videotaped messages at visits 1, 2 and 3. According to the informed consent approved by the UI IRB, "You (study participant) may feel uncomfortable in answering certain questions and you can choose to decline any aspect of the study at any time. You and your child may discontinue participating at any time without any negative consequences." Therefore, participants may choose not to complete the nine-month follow-up questionnaires.

- Each child will be examined at 12, 24 and 36 months of age (visits 2, 3 and 4) for visible plaque and dental caries by one of the examiners who will be blinded to participants' group assignment. We will utilize the d₁d₂₋₃ mfs caries criteria for scoring dental caries for the children.
- Plaque samples will also be obtained from all participating children at visits 2, 3 and 4. Numbers of MS will be derived for each sample through the standard matrix counting methodology of the spiral plating system. Plaque samples will be obtained by using sterile cotton swabs; all teeth surfaces will be swabbed. Cotton swabs will be immersed in sterile transport fluids and kept cold for transport to the microbiology labs. All laboratory procedures will be done by an experienced research scientist and under the overall guidance of [name], Professor of Microbiology & Infectious Diseases. [name] will routinely audit the database and reconcile it to a logbook that has the identification numbers for the samples stored in the ultralow freezer on a monthly basis.

Detailed Description of the Study Intervention

This is a two-arm, randomized controlled clinical trial that will compare the efficacy of autonomy-supportive videotaped oral health messages framed by SDT to more traditional neutral videotaped messages. We intent to recruit pregnant mothers enrolled in Iowa Women, Infants and Children (WIC) Supplemental Nutrition Programs and follow them until their future child is 36 months old. The primary outcome of interest will be children's caries status. Secondary outcomes will be changes in children's oral health behaviors conducive to better oral hygiene and dietary habits, as well as lower levels of dental plaque and MS.

Assuming an effect size (treatment difference) of 1.1 (standard deviation 3.45) for the number of cavitated, missing or filled lesions, Type I error level of 0.05, and 80% power, required sample size is 156 children per group at the three-year follow-up. Given enrollment of 317 mother-child dyads for each group (SDT video or neutral control), and a conservative annual attrition rate of 21%, 156 dyads per group (312 total) would be expected to complete three-year follow-up. Subjects, clinical examiners, and statistical analysts will be blinded with respect to treatment allocation. A block-level randomization scheme with a 1:1 allocation ratio will be used to determine interventions for individuals. Random block sizes of 2, 4, and 6 will be used to create the randomization scheme. Randomization will be stratified on primary language and site to ensure balance between the intervention groups. There will be 12 possible sites in the study. In addition to the CTRA, RAs will not be blinded so that they can deliver the assigned intervention.

Enrollment may take as long 18 months. Study participation will last approximately 42 months. We intent to enroll 317 pregnant mothers for each group: Group 1 (experimental - SDT)/Group 2 (neutral control). There will be four visits at the WIC clinics with three follow-ups after each WIC site visit. Outcomes will be measured at each study time points. Data will be collected in person at the WIC site visits and through completion of questionnaires through REDCapTM at follow-ups after each WIC visit. Visit 2, 3 and 4 will be scheduled based upon the child's DOB and will take place when the child is approximately 12, 24 and 36 months of age. Children will be examined (visits 2, 3 and 4) for visible plaque and dental caries by one of the study examiners who will be blinded to the participant's group allocation. Plaque samples will also be obtained from all participating children at visits 2, 3 and 4. Numbers of MS will be derived for each sample through the standard matrix counting methodology of the spiral plating system.

Detailed Description of the Study Procedures

The table below details the study procedures:

Visit	Time	Window	Purpose and Activities	Location
1.0	Visit 1	Day 0	Enrollment, informed consent, group randomization, pre-intervention questionnaires, video 1 message, post- video HCCQ and Internalization questionnaires	WIC Clinic
1.1	1 month	+8 weeks	Post-intervention questionnaires	Links via REDCap™
1.2	3 months	+6 months	Booster video 1 message	Links via REDCap™
1.3	9 months	+8 weeks	Post-intervention questionnaires	Links via REDCap™
2.0	Visit 2	1 year + 2 months	Pre-intervention questionnaires, video 2 message, post-video HCCQ and Internalization questionnaires, child's dental exam and plaque sample	WIC Clinic
2.1	1 year & 1 month	+8 weeks	Post-intervention questionnaires	Links via REDCap™
2.2	1 year & 3 months	+6 months	Booster video 2 message	Links via REDCap™
2.3	1 year & 9 months	+8 weeks	Post-intervention questionnaires	Links via REDCap™
3.0	Visit 3	2 years ± 2 months	Pre-intervention questionnaire data, video 3 message, post-video HCCQ and Internalization questionnaires, child's dental exam and plaque sample	WIC Clinic
3.1	2 years & 1 month	+8 weeks	Post-intervention questionnaires	Links via REDCap™
3.2	2 years & 3 months	+6 months	Booster video 3 message	Links via REDCap™
3.3	2 years & 9 months	+8 weeks	Post-intervention questionnaires	Links via REDCap™
4.0	Visit 4	3 years ± 2 months	Post-intervention questionnaires, child's dental exam and plaque sample	WIC Clinic

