6.4 STUDY INTERVENTION/EXPERIMENTAL MANIPULATION ADHERENCE

When the participating pregnant WIC mother is randomly assigned to one of the two study groups through a randomization algorithm conducted through REDCapTM, based on her language preference (English vs. Spanish), the subject will be linked to her assigned group and study activities in all time points throughout the duration of the study. In addition, the Data Base Manager and CTRA will keep a separate electronic log and verify any potential compliance issues through monthly data reports created by REDCapTM.

Participants will complete pre- and post-intervention questionnaires via REDCapTM at each of the four study visits at the WIC sites. In addition, participants will be sent links with follow-up questionnaires at one and nine months after each visit via texts/emails through REDCapTM. Mother's will have up to eight weeks to complete the one- and nine-month questionnaires. REDCapTM will send reminder text messages and emails at one week, two weeks and three weeks for non-responders of the one- and nine-month questionnaires. If mothers do not complete the questionnaires after the first three reminders, REDCapTM will notify the study team, and an RA will contact the mother to complete the questionnaires. Non-responders will also be mailed paper copies of the questionnaires with a prepaid and self-addressed envelope to return once completed.

It is mandatory that study subjects participate in the first visit at the WIC site for enrollment, informed consent and randomization. In addition, in order to participate in all post-intervention activities (i.e., one- and nine-month questionnaires and 3-month booster message), it is mandatory that subjects complete the assigned group intervention activities at the WIC site visit. For example, if a study subject misses a WIC site intervention (visits 1, 2 or 3), they will not complete the post-intervention activities related to the missed visit but will be scheduled for the next WIC site time point intervention.

Birth to Three – Cavity Free: Effectiveness of a Psychoeducational Intervention for ECC Prevention Protocol

Version 0.7 2 July 2024

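### The nine-month questionnaire window overlaps the next visit window, so some video 2 forms can be answered after video 3 and some video 3 forms after the Visit 4 exam

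*Protocol*

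**What the plan says.** Section 6.1.2 of the Protocol uses two different clocks.

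- **Visits** follow the child's age: "Visit 2, 3 and 4 will be scheduled based upon the child's DOB". The procedures table gives Visit 2 as one year with a two-month tolerance either side, Visit 3 as "2 years ± 2 months" and Visit 4 as "3 years ± 2 months".
- **Questionnaires** follow the video: "In order to assess long-term behavioral changes, all study mothers will be asked to complete again the post-intervention questionnaires" nine months "after viewing the videotaped messages at visits 1, 2 and 3". The table gives this form a window of +8 weeks, and section 6.4 agrees: "Mother's will have up to eight weeks to complete the one- and nine-month questionnaires".
- **Boosters** are also counted from viewing, at three months with a window of +6 months.

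The nine-month form has a stated scientific role. Section 4.1 says that "these hypothesized benefits will apply to both short-term (one-month) and long-term (nine-month) effects across each time point", and section 4.3 uses the follow-up forms to judge retention of what was presented at each intervention. Maternal knowledge and behaviour are also the mediators in the secondary objectives.

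Sections 5.5, 6.4 and 7.3 say what happens when a visit is missed: the follow-up activities tied to it are dropped. None says what happens to a form or booster link that is still open when the next visit takes place as planned. Sections 5.5 and 6.4 also have paper forms mailed to non-responders, so expiry of an electronic link alone would not settle the matter.

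**The concern.** A nine-month form for video 2 is meant to show what remains of video 2. If the mother has already seen video 3, her answer reflects both messages, and the label long-term effect of video 2 no longer describes what was measured.

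For video 3 the issue is order, since Visit 4 has no video. A form answered after the Visit 4 exam records the mediator after the outcome. Section 2.3.2 says mothers are told the child's caries status at each exam age, so the answer may be given with the result known. The mediation analysis in section 9.4.3 needs the mediator to come before the outcome, and its improved or not improved coding of behaviour relies on a clear before and after.

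At stake is the meaning of the secondary and mediator measures labelled as nine-month effects of one message.

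**Working it through.** The protocol states no figure for this overlap, so there is none to reproduce. The check is arithmetic on the windows.

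**Inputs.** Visit windows, the +8-week form window and the +6-month booster window come from the 6.1.2 table; the anchors come from the 6.1.2 text; the timing of Visit 1 (16 to 36 weeks of gestation) comes from section 4.1. One month is taken as 30.4375 days, so 8 weeks = 56 / 30.4375 = 1.84 months, and the form is open from 9.00 to 9 + 1.84 = 10.84 months after viewing.

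**Step 1. Nominal times (age of child in months).**

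| Item | Opens | Closes | Next visit may start | Overlap |
|---|---|---|---|---|
| Video 2 form | 12 + 9 = 21.00 | 22.84 | Visit 3 at 22 | 0.84 |
| Video 3 form | 24 + 9 = 33.00 | 34.84 | Visit 4 at 34 | 0.84 |
| Booster 2 | 12 + 3 = 15 | 21 | Visit 3 at 22 | none (1 month clear) |
| Booster 3 | 24 + 3 = 27 | 33 | Visit 4 at 34 | none (1 month clear) |

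**Step 2. The two clocks combined.** Consecutive visits are 12 ± 4 months apart, that is 8 to 16. Take Visit 2 at 14 months and Visit 3 at 22, both in window. The nine-month form for video 2 runs from 14 + 9 = 23.00 to 24.84, so it opens one month after video 3. The one-month form for video 3 runs from 22 + 1 = 23.00 to 24.84, which is the same window. A mother could answer both on one day, one recorded as a long-term effect and the other as a short-term effect. The booster for video 2 stays open until 14 + 9 = 23.00, also after video 3. That booster overlap requires visits less than 9 months apart.

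**Step 3. Video 1.** Visit 2 comes at least 10 months after birth. The form closes 10.84 months after Visit 1, so overlap needs delivery within 0.84 month (about 3.7 weeks) of Visit 1 and an early Visit 2. With Visit 1 at 36 weeks and delivery at 40, the earliest Visit 2 is 0.92 + 10 = 10.92 months later: no overlap. With delivery at 37 weeks it is 0.23 + 10 = 10.23 months later: an overlap of 0.61 month. Booster 1 closes at 9 months and cannot overlap.

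**Step 4. How often the next visit could come before the form closes.** The protocol gives no distribution of visit dates. Assume they are independent and uniform within the window.

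- Within ±2 months: P(interval < 8 + x) = x² / 32. For 10.84 months, x = 2.84 and P = 8.07 / 32 = 25%. For 9 months, x = 1 and P = 1 / 32 = 3%.
- Within ±1 month: P(interval < 10 + x) = x² / 8. For 10.84 months, x = 0.84 and P = 0.71 / 8 = 9%. No interval is under 9 months.

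**Step 5. From intervals to forms.** A form is affected only if it is answered after the next visit. Keeping the ±2-month assumption:

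- Completion spread evenly over the 8 weeks: average x² / 32 for x from 1 to 2.84 = (22.91 − 1) / (96 × 1.84) = about 12%.
- Completion spread evenly over the first 3 weeks (0.69 month): x from 1 to 1.69, (4.83 − 1) / (96 × 0.69) = about 6%.

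**The case against.** The strongest reply is that little of this reaches the trial's main result. Both arms have the same windows, and section 6.4 keeps each mother in her assigned arm throughout, so a later video is of the same style as the earlier one. The primary analysis is intention to treat on caries. This stands. A reader might infer that the overlap biases the randomised comparison or the primary outcome; the documents do not support that.

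A reader might also infer that every message is mixed with the next dose. That goes too far: video 3 has no successor, video 1 is affected only when delivery closely follows Visit 1, and mixing with a later video is a realistic prospect only for video 2. Nor should the booster be put on a level with the form. It never overlaps at nominal times, needs an interval under 9 months (3% on the uniform assumption) and then late viewing. A booster watched after the Visit 4 exam could matter only for the per-protocol set in section 9.3, which is a sensitivity analysis.

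The 25% should not be read as the share of contaminated forms. It counts intervals, and the reminders at one, two and three weeks should bring most answers forward. If visits only ran late, uniformly from 0 to +2 months, the interval figure would be 9%, with none under 9 months. It can also be said that the videos are specific to age, so video 3 may not teach what the video 2 form asks; the protocol does not settle this.

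Finally, analysis windows are commonly left to the statistical analysis plan, and link expiry to the database build. That does not dispose of the point, because the protocol itself fixes windows that overlap even at nominal times. An analysis rule can discard a late form, but cannot restore the order in which it was collected.

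**Conclusion.** The point holds in a limited form. The nine-month form overlaps the next visit by 0.84 month at nominal times, for both video 2 and video 3. Under the text's own anchors the video 2 form can open a month after video 3. The protocol has no closing rule.

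The consequence is that some forms labelled as the nine-month effect of video 2 would be answered after video 3, and some video 3 forms after the Visit 4 exam. This blurs the message-specific nine-month secondary measures and the order of mediator and outcome. The comparison of the two whole programmes remains valid, and the primary caries outcome is hardly touched.

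The overlap follows from the windows alone. Its frequency rests on assumed visit timing: at most about 25% of intervals with uniform ±2-month visits, about 9% with ±1 month, and fewer forms than intervals in either case.

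**What to change.** In the procedures table and section 6.4, state that a nine-month form still outstanding at the next WIC visit, whether link or paper, is completed at that visit before the video and exam, or closes then. Add that a form completed after the next video or exam is not counted as the nine-month outcome of the earlier message. This takes a table footnote, a REDCap setting and one sentence on analysis windows. The cost is a few late forms becoming missing.

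Separately, the booster window, the ±2-month visit windows (both in 6.1.2) and the two-month rescheduling allowance (5.5 and 7.3) should be reconciled with one another. That should include whether the rescheduling allowance lies inside the visit window or on top of it, and what happens to an open booster link once the next visit has taken place. Which schedule to adopt is for the investigators.
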